4.8 Recruitment, study procedures and data collection

Recruitment procedure

Talking Therapies site identification process

- Chief Investigator and researchers will contact NHS Trusts in the Yorkshire and the Humber Virtual Talking Therapies Providers Network via: 1) a short presentation in one of the network meetings and 2) an email with the research proposal inviting them to be involved in the trial.
- Researchers will circulate a research proposal (Appendix) within Talking Therapies sites via email, and request managers interested in collaborating to express an interest. They will also be asked to identify and fill in a contract naming a specific person as a Local Principal Investigator who will act as liaison between our research team and each Talking Therapies site (Appendix).
- The Research Team will organize a meeting with potential Talking Therapies site managers and potential Local Principal Investigators to explain the study, answer any questions, and seek participation and informed consent at Talking Therapies site level. We will send the protocol for sites to make an assessment of capacity and capability, and the sponsor will send a local information pack with the site file, the practicalities of delivering the study and list of roles and responsibilities. A contract agreement will be signed by the sponsor of the study and local R&D/R&I sites.
- After this, Talking Therapies sites will proceed with recruitment of therapists.

Therapist recruitment process

- Local Principal Investigators at each participating Talking Therapies sites will email copies of the participant information sheet (Appendix), consent form (Appendix) and short questionnaire (Appendix) to all therapists conducting initial assessments in their service. This letter will describe the study in general terms and explain what study participation involves as well as the voluntary nature of participation. Local Principal Investigators may also promote the study at their local team meetings (or delegate this task to a colleague). Talking Therapies site collaborators and therapists will also be invited to email or call a member of the research team if they have any further thoughts or questions after team meetings.
- Local Principal Investigators at each Talking Therapies site will invite all their therapists to participate, but any decision to participate in the study will be contracted directly between the therapist and the principal investigator. Therapists will not be pressured by their managers to participate, nor given additional incentives to do so. Therapists will have at least 1 week to consider their participation and to contact the research team to clarify questions, if necessary, prior to the deadline for submitting consent forms.

- Those wishing to participate will be asked to sign electronically the consent form (document will be uploaded on an online platform) sent directly to the research team at the Grounded Research Team. Local Principal Investigators will not receive process consent forms, which will minimise administrative burden but also minimise the potential for selection biases or undue pressure (e.g. therapists feeling that they must consent to participate if their manager is receiving consent forms).
- Consenting therapists will then be invited to participate in a training event (detailed in the study procedure section).

Patient recruitment and consent process

- Participating therapists will log in with a therapist ID in the TherapyMatch-D computer programme, and input the patient pseudonym (non-identifiable ID automatically generated by each of the electronic patient records routinely used in Talking Therapies sites). The TherapyMatch-D computer programme will then guide therapists through a brief and standardised script to provide information and seek verbal consent from patients who they assess in routine care. The script is described in an Appendix. The recruitment script will be read to all patients assessed by participating therapists, during the assessment contact. Patients will have the opportunity to ask any questions about the study and then they will be asked verbally if they provide informed consent or opt out of the study. Participants will record informed consent in the patient's clinical records.
- If they consent, participants will be asked if the assessing therapist can send them information via email or text about how their data is used by the Talking Therapies service, how to opt-out and how to contact for further questions (the participant information sheet). This link will also include information about the substudy consisting of a semi-structured interview on their view of the treatment selection process (see substudy research protocol, and Appendix on verbal consent process).
- Email will be preferable, but text has been included as an option for inclusion of participants who may not communicate via email. If patients provide their consent, the assessing therapist will send the information sheet for participants via email or text (using a link) within 1 week of their assessment by the assessing therapist.
- If participants refuse to take part in the research, therapists will record the patient's ID in the 'optout' section of the TherapyMatch-D computer programme for record purposes. The computer programme will keep a log of how many individuals how many are invited to participate, how many were eligible, and how many refuse.

Study procedure

Organisation of training event

- The research team will liaise with Local Principal Investigators to organise a virtual training session which will be accessed by all therapists regardless of treatment allocation. Training events will be run prior to the start of the study, following a standard training agenda and materials. Researchers will explain the background of the research, the aim and the process on how to use the TherapyMatch-D computer programme, as well as the fundamentals of Good Clinical Practice to gain verbal consent. Consenting therapists will have at least 3 weeks' notice about the training date, to ensure they are able to make necessary arrangements to attend. The training will take approximately 3 hours.
- The research team will produce randomly generated therapist ID numbers to ensure therapist data is fully anonymized and will be given to each therapist prior to the commencement of recruitment of patients.

Intervention: Recommendations for Treatment Selection

At the assessment session, the procedure for treatment selection in the TherapyMatch-D group will be:

- After gaining informed consent, therapists will directly input patient's anonymized data with their unique participant ID to the *TherapyMatch-D* computer programme, and patients pseudonym ID. The electronic care record system used in Talking Therapies sites autonomically assigns each patient a unique pseudonym ID which therapists will be asked to enter this at the beginning of the survey. This list of pseudonyms from *Digital TherapyMatch-D* will be held by the Grounded Research Team (Talking Therapies sites/therapists will not have access to this information), and only each care team will be able to link the pseudonym with the specific patient care record.
- Therapists will have undergone prior training on how to use this tool adequately (see organization of training event). The *Digital TherapyMatch-D* computer programme will be programmed with the targeted prescription algorithm developed in prior research and will provide a treatment recommendation in differential response cases.
- Therapists will be trained to explain their recommendation to patients in a way that shares the current available evidence behind this recommendation, but also enables shared decision-making and which considers patients' preferences. A script will be provided to therapists (Appedix) and shown on the TherapyMatch-D computer programme so therapists may adhere to the script.
- In Talking Therapies sites where there are additional High Intensity Therapies on offer (besides CBT or PCE-CfD), patients will be given a treatment recommendation if there were any, and then follow the same shared decision making to select suitable treatment.
- Due to additional factors guiding treatment selection, not all treatments selected in differential responders will match the optimal treatment recommended. Consequently, the trial will use an intent-to-treat approach. In the Digital TherapyMatch-D, therapists will also be asked to record the actual treatment selected, and the rationale where the recommended treatment and the selected treatment do no match to monitor the factors that led clinicians and patients to choose a different treatment.
- Cases without a differential response identified will not be provided with any treatment selection recommendations, and therefore will follow AAU.

At the assessment session, the procedure for treatment selection in the AAU group will be:

- Therapists will follow the same procedure as above where they input fully anonymized clinical data during the initial assessment into the treatment selection computer programme Digital TherapyMatch-D.
- All cases, including differential response cases, will use the routine treatment allocation process
 which consist mainly shared decision making between therapist and client, alongside clinical formulation
 by the assessing therapist, treatment availability, and clinical supervisor's recommendations.

Outcomes, data collection and safeguarding procedures

Talking Therapies services routinely monitor clinical outcomes by asking patients to complete brief standardized symptom questionnaires on a session-to-session basis, which is standard practice (Clark, 2011). These questionnaires are collected by therapists and results are routinely entered into an electronic case record system. All data collection at an item level will be part of routine outcome monitoring except for the semi-structured interviews.

Across both groups (TherapyMatch-D and AAU), patients' data will be collected at the following points in time:

- At assessment, as is routine treatment, patients will be asked to complete the following outcome measures: PHQ-9, GAD-7, WSAS, Outcome expectancy, Personality profile, as well as to provide clinical and demographic variables (detailed in outcome measures).
- Throughout treatment, CBT and CfD therapists will input routinely collected data at each session from the primary and secondary outcome measures to patient record systems used in routine care (e.g., SystemOne and Insight). The research team will also work with a data manager at each of the participating Talking Therapies sites to download a pseudo-anonymized and aggregated dataset from patients, excluding data from patients that did not provide consent. The dataset will include patient-level clinical data nested within therapist caseloads (which will be linked to a unique participant ID).

Throughout treatment, any serious adverse events (SAE) will be reported by the therapist to the Local Clinical Collaborator. Adverse effect is defined as an untoward occurrence that results in death, is lifethreating, requires hospitalisation or prolongation of existing hospitalisation, results in persistent or significant disability or incapacity, consists of congenital abnormality or birth defects, or is otherwise considered medically significant by the investigator (in line with Safety Reporting for Research other than Clinical Trials of Investigational Medical Products for UK Health Departments' Research Ethics Service (RES) by the Health Research Authority (HRA; 2022). While we do not envision adverse effect related to the current trial for the reasons outline above, as a pilot trial, we will record both serious adverse events (SAE) and non-serious adverse events as defined by the National Research Ethics Service and report them to the appropriate research committee and to take appropriate action. Any serious adverse events (defined by HRA, 2022) should be reported by anyone immediately to the Local Clinical Collaborator who will inform the Chief Investigator upon becoming aware of them, and within 24 hours and following the Good Clinical Pratice (GCP) Guidelines. The local Clinical Collaborator will report within 3 days to the Chief Investigator if it is not urgent, and immediately by telephone if it requires urgent safety measures. The Chief Investigator will discuss within one week with the trial steering committee holding oversight of the study, where researchers alongside the sponsor/committee will seek to determine if a serious adverse event is related to the trial (resulted from administration of any of the research procedures) and unexpected (not listen in the protocol as an expected occurrence). All opinions from the Investigators and Sponsor/Committee will be reported to the Research Ethics Committee within 15 days of the Chief Investigator becoming aware of the event.

Fully encrypted data will be transferred from each Talking Therapies site service to the research team using a secure electronic file transfer. The dataset will be stored in a University of Sheffield secure network drive, which has restricted access to members of the research team. This will ensure the security and adequate storage of research data, consistent with NHS and academic codes of information governance and data protection.

All analyses will be carried out using University of Sheffield computers with up-to-date security software, and data will be held in a restricted-access drive. The study dataset will be held at the University for 10 years after the conclusion of the study.

The end of the data collection will be approximately when the last recruited participant completes their treatment pathway (we envision a total of 2-year active study period). The study will be considered as finalised once the data analysis has been completed as well as the dissemination reports (6 to 12 months after data collection has finished).

5. Data analysis

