4.1. Study Design Overview

[figure not shown]
The proposed study is a pilot cluster pragmatic multi-site randomised controlled trial (RCT). Participants will be adults with depression symptoms who seek help at one of the study sites and are suitable for high intensity psychological therapies.

Each participating Talking Therapies site will be stratified according to sociodemographic characteristics and randomly assigned to one of the arms of the RCT: TherapyMatch-D versus AAU. Therapists across both arms will be imputing all consenting patient's data into the TherapyMatch-D computer programme. However, 30% of the cases are expected to show a differential treatment response to treatment according to prior literature (Delgadillo & Gonzalez Salas Duhne, 2020) which are the main group of interest. Differential responders will be identified using the AI targeted prescription algorithm from prior research embedded in the TherapyMatch-D computer programme, and these will the only cases included in the primary data analysis.

In TherapyMatch-D sites, during the initial assessment, differential response cases will be provided with a treatment selection recommendation about their optimal treatment based on the targeted prescription algorithm to be used alongside shared decision making. In AAU sites, during the initial assessment, differential response cases will use only shared decision making to guide treatment selection as occurs routinely in primary care. Non-differential response cases across both arms of the CT will also use only shared decision making to guide treatment selection as per routine care.

Following the initial assessment and treatment selection, subsequent psychological care provision across TherapyMatch-D and AAU (i.e., CFT or PCE-CfD) will be delivered without changes to routine care provision, with the exception of an additional semi structured interview for a subset of patient, as part of a substudy (separate protocol for substudy).

Figure 1. Study flow diagram

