Adverse events. We will record serious and non-serious adverse events such as deaths, self-harm, serious violent incidents, referral to crisis care or admission to psychiatric hospital within both groups. Serious adverse effects related to the trial and unexpected (in accordance with the Health Research Authority guidelines; HRA, 2022), will be reported by Chief Investigator to the appropriate research committee to take appropriate action. The trial relies on standard treatment already provided routinely within primary care services, and all treatments delivered as evidence-based, not experimental. The trial is not changing how the treatment is delivered, and therefore risk management procedures will follow standard Talking Therapies procedures. Although we do not expect adverse effects related to the trial, we will compare rates of reliable deterioration in patients across both arms of the trial to quantify any adverse effects related to the trial.

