5.1. Sample size calculation

Pilot trials do not require a formal sample size calculation. However, a sample of at least 64 participants per arm is desirable (Teare et al., 2014) for a binary outcome in a pilot trial. We will aim to recruit 6-10 clusters (3-5 sites randomised in each arm) to allow subsequent sample size calculation for a definitive RCT. Within each Talking Therapies site, we will aim to recruit a minimum of 1 therapist that carry out routine assessment (maximum of 2 therapists per site). Each Talking Therapies site will aim to recruit 64 patients, For this, a total of 432 patients would be screened (216 patients per arm). As we expect approximately 30% of patients across sites to have a differential response, we estimate there would need to be 216 patients screened (64 patients per arm; 216*30% = 64). This calculation is based on the assumption of equal availability for treatment. As a pilot trial, any differences in treatment offer and waiting time for the different treatments will be reported and considered for potential subsequent research.

Overall, we will aim to recruit a minimum of 6-10 therapists that carry out routine assessments across the 6-10 Talking Therapies services (1 to 2 per Talking Therapies service). Between the 6 to 20 therapists, we expect that they will assess at least 432 during a 1-year study period, which would require each therapist to assess 1 to 2 cases per week on average.

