4.3. Secondary analyses

The above modelling strategy will be repeated to compare the rate of improvement (RCSI) in GAD-7 anxiety symptoms, and RCSI in depression symptoms only in the cases who attended at least one treatment session. We will also compare outcome expectancy, dropout rates and adverse effects between groups, and compare characteristics between those who attended at least one treatment session versus those who dropped out following assessment. For both TherapyMatch-D and control groups, we will estimate the proportions of participants who had RCSI post-treatment, and who completed/dropped out of treatment. We will also calculate and report effect sizes for each of the symptom measures (PHQ-9, GAD-7, WSAS) using Cohen's *d* metric (Cohen, 1988), based on mean differences between groups. Treatment attendance, completion, and dropout rates will be presented diagrammatically and based on CONSORT guidelines. To quantify any potential adverse effects related to the trial, we will also calculate a rate of reliable deterioration in patients across both arms of the trial. Further, we will use the data collected to identify complex cases (see StratCare Trial from Delgadillo et al., 2021) and control for variability in complex cases across Talking Therapies sites.

We will examine adherence to the TherapyMatch-D model using the full study sample of participants with a differential treatment response across both arms. Each therapist's Treatment-Matching Precision Score (TMaP) will be calculated, which is a statistical measure of agreement between their observed treatment selection and the recommendations made using the prognostic algorithm. In the experimental group, this would represent the agreement of patients accepting the recommended treatment. In the control group, this is the post-hoc analysis of the agreement the optimal treatment that the prescriptive algorithm would recommend (which patients did not receive, since they were in the control group) and the actual treatment selected via shared decision making. A comparison of mean TMaP scores between groups will be done using parametric or non-parametric tests, depending on the distribution of TMaP scores.

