Further, we will record both serious and non-serious adverse events as defined by the National Research Ethics Service (e.g., deaths, self-harm, serious violent incidents, referral to crisis care or admission to psychiatric hospital) within both groups, report them to the appropriate research committee and to take appropriate action. Any serious adverse events (defined by HRA, 2022) will be reported by the therapist to the Local Clinical Collaborator. The Local Clinical Collaborator will report within 3 days to the Chief Investigator if it is not urgent, and immediately by telephone if it requires urgent safety measures. The Chief Investigator will discuss within one week with the trial steering group, where independent researchers will aid the decision making if a SAE is related to the trial (resulted from administration of any of the research procedures) and unexpected (not listen in the protocol as an expected occurrence). If the SAE is deemed to be related and unexpected, the Chief investigator will report to the Research Ethics Committee within 15 days of the Chief Investigator becoming aware of the event.

The trial relies on standard treatment already provided routinely within primary care services, and all treatments delivered as evidence-based, not experimental. The trial is not changing how the treatment is delivered, and therefore risk management procedures will follow standard Talking Therapies procedures. Although we do not expect adverse effects related to the trial, we will compare rates of reliable deteriorate in patients across both arms of the trial to quantify any adverse effects related to the trial.

There will be a trial steering committee to ensure governance in accordance with Data Monitoring and Ethics Committee (DMEC) guidelines. Researchers will invite independent researchers with expertise in the field of RCTs in mental health. They will meet regularly to ensure ethical and safe procedures, and any adverse events will be discussed in this Committee.

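### The adverse-event rules conflict and fix no capture period from assessment, so events before the first session and in non-starters may be under-ascertained

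*Protocol*

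**What the plan says.** **When the intervention acts.** Protocol 4.1: "In TherapyMatch-D sites, during the initial assessment, differential response cases will be provided with a treatment selection recommendation". The therapy that follows is delivered as in routine care in both arms.

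**Safety as an outcome.** Section 3.2 lists adverse events among the secondary objectives. Section 4.7 says "We will record serious and non-serious adverse events such as deaths, self-harm, serious violent incidents, referral to crisis care" and admission to psychiatric hospital, in both groups. The secondary analyses (in section 5, but headed 4.3) compare adverse effects between groups and add a rate of reliable deterioration by arm as a gauge of trial-related harm.

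**Who reports, and when.** Section 4.8 opens its safety paragraph with "Throughout treatment, any serious adverse events (SAE) will be reported by the therapist to the Local Clinical Collaborator". Further down, the same paragraph says that serious events "should be reported by anyone immediately to the Local Clinical Collaborator". Section 6.3 says "Any serious adverse events (defined by HRA, 2022) will be reported by the therapist to the Local Clinical Collaborator", with no period and no mention of other reporters.

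**The interval between assessment and therapy.** Section 5.1 says "any differences in treatment offer and waiting time for the different treatments will be reported". The secondary analyses plan to "compare characteristics between those who attended at least one treatment session versus those who dropped out following assessment". The protocol therefore allows for a wait and for patients who never begin therapy.

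**The concern.** The only thing the trial changes is what happens at assessment. Harm related to the trial procedure could arise from that moment on, including while a patient waits for the selected therapy or after a patient decides not to start. The one explicit period attached to reporting is the course of treatment, and the named reporter is the therapist. A patient who is waiting, or who has left before the first session, has no stated contact with a therapist.

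Adverse events are compared between arms in a trial analysed by intention to treat. If finding an event depends in practice on having started therapy, an arm with more non-starters or longer waits could look safer because fewer of its events come to light. This is a pilot meant to inform a definitive trial, so a capture procedure with this weakness could be carried forward.

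**Working it through.** The plan states no figure to reproduce here. The check is of the text, followed by arithmetic on assumed values to show scale.

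**1. The reporting rules side by side**

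| Place | Reporter | Period | Events covered |
|---|---|---|---|
| 4.8, first rule | therapist | during treatment | serious |
| 4.8, second rule | anyone | none stated | serious |
| 6.3 | therapist | none stated | serious |
| 4.7 and 6.3, general statements | not stated | none stated | serious and non-serious |

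No row gives a start at consent or assessment, or an end. For non-serious events there is neither a reporter nor a period.

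**2. Does treatment, in 4.8, include the wait?** The list of data-collection points in 4.8 has assessment and treatment as separate items, and the treatment item is about sessions. The natural reading leaves the wait out.

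**3. Is there contact during the wait?** Section 6.3 places the therapist's questionnaire review at the initial assessment and at each session. Nothing is described between them.

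**4. Does another source fill the gap?** The care-record and service-use fields listed in 4.7 and 6.2 include diagnoses, number of sessions, treatments offered, reason for discharge and last step reached. Adverse events are not listed. Reliable deterioration needs a score after assessment. Section 4.8 collects those scores at sessions, so non-starters would normally have none.

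**5. Scale, on assumptions.** The protocol gives treatment length T as 4 to 6 months (4.3). It gives no wait w and no non-start share d, so w = 1 to 3 months and d = 10% to 30% are assumed. Suppose that capture took place only on treatment, and that starters and non-starters are followed for the same w + T months:

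Uncovered share of person-time = 1 − (1 − d) × T / (w + T)

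- Lowest: w = 1, T = 6, d = 0.10 gives 1 − 0.90 × 6/7 = 0.229, about 23%.
- Highest: w = 3, T = 4, d = 0.30 gives 1 − 0.70 × 4/7 = 0.600, or 60%.

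Non-starters per arm: 64 × 0.10 = 6.4 to 64 × 0.30 = 19.2 of the differential responders, and 216 × 0.10 = 21.6 to 216 × 0.30 = 64.8 of all screened patients.

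For given w, T and d, this share is a ceiling on what the window costs, because it gives the open-ended rule in 4.8 no credit at all.

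**The case against.** Several stronger conclusions are tempting, and the documents do not support them.

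- **That events outside treatment are missed, because treatment is the sole window.** The second rule in 4.8 lets anyone report a serious event, with no period and no condition that therapy has begun. The rule in 6.3 carries no period either. Some events in waiting patients would reach the trial by these routes.
- **That the safety comparison covers starters only.** The secondary analyses compare adverse effects between groups with no attendance condition. The analysis restricted to patients with at least one session concerns improvement in depression, not safety.
- **That the protocol expects waits to differ.** Section 5.1 assumes equal availability and undertakes to report any differences, which is contingent.
- **That one arm can be given a long wait and the other a short one.** Waiting belongs to the therapy and the site, and both arms use both therapies. About 30% of patients in the experimental arm get a recommendation. It can point either way and can be declined. If the therapies had assumed waits of 1 and 3 months, and every recommended patient moved the same way, the mean wait over all consenting patients in that arm would change by 0.30 × (3 − 1) = 0.6 months.

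It is also fair to say that the time points for reliable deterioration may be set in a statistical analysis plan not shown here, that the data-manager download already exists and includes reason for discharge, and that this is a pilot of choosing between two routine therapies with no hypothesis testing.

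What these arguments leave untouched is the gap in active capture. The open-ended rule is passive: someone must learn of the event and connect it with the trial. It covers serious events only, and 6.3 does not repeat it. Nobody is assigned to look for events in waiting patients or non-starters.

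**Conclusion.** The point holds as a risk of under-ascertainment. Section 4.8 contains two unreconciled reporting rules, 6.3 names only the therapist, no capture period from consent or assessment is fixed, and no active route is described for finding serious or non-serious events before the first session or in patients who never start.

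The shortfall could differ by arm if the recommendation alters who waits or who starts. Neither its direction nor its size can be derived from the protocol. The range of about 23% to 60% of person-time rests on the assumed waits and non-start shares and on capture confined to treatment. It is not an estimate of events lost or of bias between arms.

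The primary outcome is unaffected. The point should still be settled in the protocol, because it concerns how a compared secondary outcome is collected and the change is cheap.

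**What to change.** 1. Reconcile the reporting rules in 4.8 and 6.3 so that both state the same reporters and the same period.
2. In both sections, define the capture window for serious and non-serious events, in both arms, as consent at the assessment contact to discharge from the service, whether or not therapy starts.
3. Add the events that 4.7 already lists (death, self-harm, serious violent incident, referral to crisis care, psychiatric admission), with dates, to the care-record download that site data managers already provide. Add these fields to the lists in 4.7 and 6.2. This gives an active route for periods when no therapist is seeing the patient.
4. In the secondary analyses, state that adverse events are compared by arm in all consenting patients, both per patient and per month since assessment.

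The cost is protocol wording, a few more download fields, and more events to log and assess, most of them unrelated to the trial. The change concerns data capture and reporting only and leaves clinical care as it is.
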